The effect of high intensity interval vs moderate continuous endurance exercise training on program adherence

Introduction & Background

For optimal health, current Canadian physical activity guidelines recommend 150 minutes of moderate intensity or 75 minutes of vigorous-intensity endurance exercise training per week. Yet many Canadians fail to meet these recommendations apparently due to lack of time. Recently, several studies observed that very brief, repeated exercise bouts at high intensity promote similar health and exercise performance benefits as those found with moderate endurance training of much longer duration. For example, MacPherson and colleagues (2011) has compared brief, sprint vs much longer continuous endurance exercise training and found similar improvements for endurance capacity and exercise performance. Similarly, Gillen et al. (2014) found three 20 second bouts of high interval training at an all-out effort intensity elicited similar physiological benefits as to 50 minutes of moderate endurance training. Further, another recent study found short, repeated bursts of high-intensity training over 12 weeks had similar health benefits as 50 minutes of moderate endurance training (Gillen et al., 2016). The current study will follow a similar exercise training protocol as Gillen et al. (2016) however, importantly, will control exercise time (20 minutes in both groups) because it is assumed that the shorter duration in the high intensity groups of previous studies may contribute to greater program adherence rates.

Research Objectives

1. To determine whether high-intensity interval training (HIIT) group experience a greater program adherence than moderate continuous endurance exercise training (MCEET) group when matched for time commitment of 20 minutes
2. To assess whether HIIT group results in greater improvements in fat loss and endurance capacity than MCEET group

Research Hypothesis

The study hypothesizes that HIIT group will result in greater program adherence than MCEET. Also, HIIT group will result in greater improvements in fat loss and endurance capacity vs. MCEET group.

Methods

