40 healthy adults aged 19 to 35 years (20 men, 20 women) will participate in the study. Participants will be recruited from Western University and its surrounding community via university poster. Interested participants will be asked to come to the Exercise Nutrition Research Laboratory ([name]) for a face-to-face interview with the investigator and to complete Get Active Questionnaire (GAQ) that includes medical history for pre-screening eligibility. Inclusion criteria include healthy participants between the ages of 19 to 35 years who engage in physical activity less than three times per week. They must be able to run a mile, have an access to the gym as well as smart phones (such as Android, Cat phone, Google Nexus, Samsung Galaxy, iPhone, Microsoft Lumia, myTouch or Phablets) and can access to Apps (such as MyFitnessPal, Rise Up, Calorific, My Diet Coach, Yazio, On The Regimen, See How You Eat, Lost It, MyNetDiary or MyPlate). Exclusion criteria include diabetic, pregnant, individuals with a history of fainting, low and high blood pressure, heart disease, respiratory disease, migraines, heartburn, smokers, engage in physical activity

more than two times per week and answering YES to any questions from page 1 of GAQ. Eligible participants will be provided with the written informed consent.

Once completed, all participants will complete body composition testing via air displacement plethysmography (Bod Pod) pre and post intervention (week 0 and 6). Following Bod Pod measurements, participants will run a practice mile run for familiarity and will run again for measurement purposes before and after the exercise intervention to assess their endurance capacity. Time will be measured by a stopwatch. Participants will be match-paired based on their endurance capacity to either HIIT or MCEET group for five weeks. They will fill out two validated questionnaires, physical activity enjoyment scale (PACES) and exercise adherence rating scale (EARS) after the 6th, 9th and 15th session to assess their program adherence. They will be instructed not to engage in any either exercise program during the study period.

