The first week of the exercise intervention will consist of one-on-one supervised treadmill training, three times per week in the lab. From week two to five, participants will follow the same exercise program on their own at their preferred gym three times per week in order to examine free-living individuals adhere to two exercise programs. Each participant will be matched to either HIIT or MCEET group based on their timed one-mile run. The HIIT group will perform six, 20-second bouts of high intensity interval exercise separated by 2 minutes of active recovery (walking) while the MCEET group will perform 14 minutes of continuous endurance exercise at 70% Maximum Heart Rate (MHR). Both exercise protocols will include 3 minutes of warm up and cool down at a 30% MHR, for a total of 20 minutes for each treatment.

Ratings of perceived exertion (RPE; Borg CR-10 scale) will be recorded at the end of each interval for HIIT group and at 10 and 20 minutes of exercise for MCEET group on the 6th, 9th and 15th session. All participants will log their heart rate before, during, and immediately after each training session using Fitbit or a free heart rate monitor mobile App (e.g. Argos) to ensure safety and achievement of their targeted heart rate. Participants will also complete physical activity enjoyment scale (PACES) and exercise adherence rating scale (EARS) on the 6th, 9th and 15th session to assess their program adherence. To accommodate progression, training intensity will be adjusted to maintain the desired relative exercise intensity based on above measurements. Finally, no attempt will be made to modify the participants daily diet, but a 3-day food log will be collected via free mobile app (e.g. MyFitnessPal) to assess food intake for any change. Completed questionnaires and the recorded heart rate data saved on Fitbit or a mobile app will be used to confirm program adherence.

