All the collected data will be statistically analyzed by Sigma Plot 12.0 (Systat Software, San Jose, CA, USA) using a two-way analysis of variance (ANOVA), Tukey's post hoc test, and a paired t-test. Significance set at $p < 0.05$. Sample size estimates are generated with a two-way analysis of variance (ANOVA). The primary outcome variable is the program adherence, with a minimum important difference of 19.6 between HIIT (103.8 ± 9.4) and MCEET (84.2 ± 19.1 ; Thum, Parsons, Whittle & Astorino, 2017). Based on the data from Kadam & Bhalerao (2010), we calculate the pooled variance (19.1), effect size f (0.8), and Cohen's d (1.96) for the sample size estimation.

Using ANOVA, match-paired study design, a minimum of 15 participants is required for an alpha of 0.05 and 95% power. 34% of drop out rate (Linke, Gallo & Norman, 2011) will be included in addition to the minimal sample size resulting in 20 participants for each group.

References

- Gillen, J. B., Martin, B. J., MacInnis, M. J., Skelly, L. E., Tarnopolsky, M. A., & Gibala, M. J. (2016). Twelve weeks of sprint interval training improves indices of cardiometabolic health similar to traditional endurance training despite a five-fold lower exercise volume and time commitment. *PloS one*, *11*(4), e0154075.
- Gillen, J. B., Percival, M. E., Skelly, L. E., Martin, B. J., Tan, R. B., Tarnopolsky, M. A., & Gibala, M. J. (2014). Three minutes of all-out intermittent exercise per week increases skeletal muscle oxidative capacity and improves cardiometabolic health. *PLoS One*, *9*(11), e111489.
- Kadam, P., & Bhalerao, S. (2010). Sample size calculation. *International Journal of Ayurveda Research*, *1*(1), 55–57. <http://doi.org/10.4103/0974-7788.59946>
- Linke, S. E., Gallo, L. C., & Norman, G. J. (2011). Attrition and adherence rates of sustained vs. intermittent exercise interventions. *Annals of Behavioral Medicine*, *42*(2), 197.
- Macpherson, R. E., Hazell, T. J., Olver, T. D., Paterson, D. H., & Lemon, P. W. (2011). Run sprint interval training improves aerobic performance but not maximal cardiac output. *Medicine & Science in Sports & Exercise*, *43*(1), 115-122.
- Thum, J. S., Parsons, G., Whittle, T., & Astorino, T. A. (2017). High-Intensity Interval Training Elicits Higher Enjoyment than Moderate Intensity Continuous Exercise. *PloS one*, *12*(1), e0166299.

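### Allocation is by matching on one-mile time alone; no random or concealed step decides which member of a pair gets HIIT

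*Combined protocol and SAP*

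**What the plan says.** Allocation is described in two sentences of the Methods. The paragraph on baseline testing says: "Participants will be match-paired based on their endurance capacity to either HIIT or MCEET group for five weeks". The paragraph on the intervention says: "Each participant will be matched to either HIIT or MCEET group based on their timed one-mile run". The sample-size text at the end of the Methods adds only a design label: "Using ANOVA, match-paired study design, a minimum of 15 participants is required for an alpha of 0.05 and 95% power".

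Three other statements bear on the point:

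- Eligibility screening includes a "face-to-face interview with the investigator", so someone on the study team has met each participant before assignment.
- Mile time is also known before assignment, since participants "will run again for measurement purposes before and after the exercise intervention to assess their endurance capacity".
- The Research Hypothesis is directional: "The study hypothesizes that HIIT group will result in greater program adherence than MCEET".

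The sample-size text names program adherence as the primary outcome. The enjoyment (PACES) and adherence (EARS) questionnaires are used to assess it, and the intervention paragraph adds: "Completed questionnaires and the recorded heart rate data saved on Fitbit or a mobile app will be used to confirm program adherence".

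The document does not mention randomisation, a sequence, concealment or the person who assigns.

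**The concern.** Matching and assignment are separate steps. Matching says who is comparable with whom; assignment says which of the two gets which program. The plan specifies only the first. One team could toss a coin within each pair and another could choose by judgement, and both would have followed the protocol.

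Objective 1 asks whether HIIT produces greater adherence than MCEET. Matching on mile time serves the endurance outcome, because mile time is its baseline value. It does not protect adherence against factors unrelated to mile time, and motivation and exercise preference are the obvious candidates. Training is unsupervised from week two to week five, so differences in motivation have room to act. If more motivated participants, or those who prefer intervals, tend to be placed in HIIT, the groups will differ in adherence even if the programs do not. A tilt the other way could hide a real HIIT benefit. No planned analysis would repair this afterwards, because the plan lists no baseline measure of motivation or preference.

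**Working it through.** **1. Reading the text.** The plan gives no figure on this point to reproduce, so the first check is of the wording.

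| Question | Baseline-testing paragraph | Intervention paragraph | Sample-size text |
|---|---|---|---|
| What are participants matched on? | Endurance capacity | One-mile time | Not stated (design label only) |
| Which pair member gets HIIT? | Not stated | Not stated | Not stated |
| Random sequence? | Not stated | Not stated | Not stated |
| Concealment? | Not stated | Not stated | Not stated |
| Who assigns? | Not stated | Not stated | Not stated |

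The Introduction, Objectives and Hypothesis add nothing on allocation.

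**2. Illustrating the stakes.** Suppose the programs have the same true effect on adherence, but selection moves one group's mean by d standard deviations. The values of d are assumed; the documents support no particular value.

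*Unpaired two-sided t-test, alpha 0.05.* The noncentrality is d × √(n/2), with 2n − 2 degrees of freedom. For example, at n = 20 and d = 0.5 it is 0.5 × √10 = 1.58. With 38 degrees of freedom the critical value is 2.02 and the rejection probability is 0.338.

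| n per arm | d = 0 | d = 0.2 | d = 0.3 | d = 0.5 |
|---|---|---|---|---|
| 20 (planned) | 0.050 | 0.095 | 0.152 | 0.338 |
| 15 (planned minimum) | 0.050 | 0.083 | 0.125 | 0.262 |
| 13 (20 × 0.66 = 13.2, after the planned 34% dropout) | 0.050 | 0.078 | 0.114 | 0.232 |

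*Paired two-sided t-test, alpha 0.05.* The noncentrality is d × √n / √(2(1 − r)), with n − 1 degrees of freedom, where r is an assumed within-pair correlation of adherence.

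| Complete pairs | r | d = 0.2 | d = 0.3 | d = 0.5 |
|---|---|---|---|---|
| 15 | 0 | 0.080 | 0.120 | 0.248 |
| 15 | 0.3 | 0.094 | 0.150 | 0.332 |
| 15 | 0.5 | 0.112 | 0.192 | 0.438 |
| 20 | 0 | 0.092 | 0.147 | 0.324 |
| 20 | 0.5 | 0.136 | 0.247 | 0.565 |

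**3. The shifts on the outcome scale.** The sample-size text gives SDs of 9.4 (HIIT) and 19.1 (MCEET) and a target difference of 19.6. The root-mean-square SD is √((9.4² + 19.1²)/2) = 15.05.

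| SD used | d = 0.2 | d = 0.3 | d = 0.5 |
|---|---|---|---|
| 19.1 | 3.8 points (19% of 19.6) | 5.7 (29%) | 9.6 (49%) |
| 15.05 | 3.0 points (15%) | 4.5 (23%) | 7.5 (38%) |

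The rates are two-sided, so a shift of the same size toward MCEET gives the same figures.

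**The case against.** The strongest reply is that the protocol is silent rather than wrong. It is very short, does not say that staff choose, and may simply have left out a random step that was intended. It does not say that the interviewing investigator also allocates, and the directional hypothesis belongs to the study, not necessarily to whoever assigns. All of this is fair. The finding is an unspecified step, not demonstrated investigator choice. But which pair member gets HIIT is the step on which the between-group comparison depends, and no other text supplies it. The protocol has to change whether randomisation was intended or not.

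Several points against the illustration also stand:

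- Every shift is assumed, so the rates show sensitivity and are not properties of this plan.
- The document names two-way ANOVA, Tukey's test and a paired t-test without saying which one tests adherence. The unpaired t-test is a stand-in.
- Converting with the MCEET SD alone gives the larger point values, so both conversions are shown.
- A within-pair correlation near 0.5 would mean that mile time is related to adherence, in which case matching gives some protection. If it is unrelated, the r = 0 rows apply.
- Self-reporting by participants who know their program is a separate measurement problem that random assignment would not cure. The heart-rate records partly address it. The allocation point does not depend on it.

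None of these supplies the missing step.

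**Conclusion.** The concern holds and should be fixed before anyone is assigned. The only stated allocation rule is matching on mile time, which cannot decide who in a pair receives HIIT; no random or concealed step is given. A difference in adherence would therefore be weaker evidence that the program caused it. That the step is absent from the text is certain. Whether selection would occur in practice, and in which direction, is unknown.

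The size of any bias cannot be derived from the documents. Under the assumed shifts of 0.2 to 0.5 SD and no true effect, the nominal 5% error becomes about 8% to 34% across 13 to 20 per arm unpaired. With 15 complete pairs and a within-pair correlation of 0 to 0.5, it becomes about 8% to 44%.

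**What to change.** In both Methods paragraphs that describe allocation, state the following:

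1. Pairs are formed on baseline mile time.
2. After both members have completed baseline testing and the pair is fixed, one is assigned to HIIT and the other to MCEET from a computer-generated random list.
3. The list is prepared in advance and concealed from the staff who enrol and pair participants until that moment.

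If randomisation was always intended, this is a clarification. If allocation is deliberately non-random, say so, describe the study as non-randomised, and limit the causal claims in the objectives and hypothesis. At a minimum the text must say how pair members are assigned. Concealment goes beyond that minimum, but it is what keeps pairing and enrolment free of foreknowledge. Pairing within sex is an optional refinement and not part of this point.

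The cost is one or two sentences and a free list. The matched design and 20 per group are unchanged. The one practical drawback is that the first member of a pair may have to wait for a match.

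### The second exertion rating in the moderate continuous arm is timed at minute 20, after the work block has ended, so a between-arm comparison that uses it would understate exertion in that arm

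*Combined protocol and SAP*

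**What the plan says.** All of this stands in the Methods of the combined protocol and SAP.

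- **Session structure (exercise-intervention paragraph).** MCEET does 14 minutes of continuous work at 70% of maximum heart rate. HIIT does six 20-second bouts with 2-minute walking recoveries between them. Then: "Both exercise protocols will include 3 minutes of warm up and cool down at a 30% MHR, for a total of 20 minutes".
- **Rating times (the paragraph that follows).** At sessions 6, 9 and 15, RPE "will be recorded at the end of each interval for HIIT group" and "at 10 and 20 minutes of exercise for MCEET group".
- **Use of the readings (same paragraph).** After RPE, heart rate and the two questionnaires have been listed, the text says that "training intensity will be adjusted to maintain the desired relative exercise intensity based on above measurements". It does not say which of these measurements is meant.
- **Analysis (statistical paragraph).** Everything collected goes into a two-way ANOVA, Tukey's post hoc test and a paired t-test. No summary or contrast is given for RPE. Program adherence is the primary outcome.

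**The concern.** The HIIT ratings are tied to an event, the end of an interval. The MCEET ratings are tied to a clock, and the second clock time is the full length of the session, not the end of the work. One arm would then be rated only on its work, while the other would have half its ratings taken after three minutes of cool-down.

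The distortion runs one way: a rating after three minutes at 30% of maximum heart rate should be lower than one given during work at 70%. A report that MCEET felt easier could therefore come partly from when participants were asked. The three rated sessions all fall in the unsupervised weeks, so nobody is present to move the rating to the end of work, and a work-period rating that was not taken cannot be recovered later.

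**Working it through.** **Inputs, all from the Methods.** Warm-up 3 min; MCEET work 14 min; cool-down 3 min; stated total 20 min; MCEET ratings at 10 and 20 min; HIIT bouts 6 × 20 s with 2 min between; rated sessions 6, 9 and 15; three sessions a week for five weeks, with week one supervised.

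**1. Reproduce the stated session length.** MCEET: 3 + 14 + 3 = 20 min, as stated. If the 3 minutes covered warm-up and cool-down together, the total would be 3 + 14 = 17, which does not match. So it is 3 minutes each, and work runs from minute 3 to 3 + 14 = 17.

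**2. Place the MCEET ratings on each possible clock.**

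| Clock starts at | 10-minute rating | 20-minute rating |
|---|---|---|
| Session start | 10 − 3 = 7 min into work | 20 − 17 = 3 min after work ends; last moment of cool-down |
| Start of work | 10 min into the 14 | session minute 3 + 20 = 23, after the session is over |

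The first rating is within the work on both clocks. The second is within it on neither.

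**3. Place the HIIT ratings.** Reading an interval as the 20-second bout, the first bout ends at 3 + 0.33 = 3.33 min and each later one 2.33 min after the last: about 3.33, 5.67, 8.00, 10.33, 12.67 and 15.00 min. None falls in the cool-down.

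**4. Count per participant.** MCEET: 2 ratings × 3 sessions = 6, of which 3 are off-work. HIIT: 6 × 3 = 18, of which none is.

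**5. Size, by assumption.** The documents give no RPE values. Let w be the work rating (taken as the same at minute 10 and at the end of work) and c the cool-down rating. If the two MCEET ratings are averaged, the shortfall is w − (w + c)/2 = (w − c)/2. Assume w from 3 to 6 and c from 0.5 to 2:

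- smallest: (3 − 2)/2 = 0.5 points
- largest: (6 − 0.5)/2 = 2.75 points

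If the ratings are analysed by time point instead, the minute-10 value is unaffected and the second carries the whole gap w − c.

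**6. Reach into training.** 3 × 5 = 15, so session 15 is the last and cannot alter later training. Only the ratings at sessions 6 and 9 could. Sessions 1 to 3 are the supervised ones, so every rated session is unsupervised.

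**The case against.** The timing itself is hard to dispute. The case on the other side concerns what follows from it.

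- **No specified comparison is at stake.** RPE is in neither objective and neither hypothesis, and it is not among the sources named for confirming adherence (questionnaires and heart-rate records). The only route to a between-arm test is the general statement that all collected data are analysed. This stands. A reader might infer that the trial's main comparison is biased; the documents do not support that.
- **Intensity adjustment may not use RPE.** A reader might also infer that the low rating will change how hard MCEET participants train. The text does not say so. The MCEET target is expressed as a heart rate, and heart rate is logged at every session to check it, so heart rate is the more natural input. This stands: the effect is possible, not established.
- **The size is assumed.** Both the RPE values and the averaging rule come from outside the documents. This stands; the direction does not depend on the particular values, provided exertion is rated lower in the cool-down than in the work.
- **The term interval is not defined.** Reading it as the 20-second bout is natural, but the count of no off-work HIIT ratings depends on it.
- **Minute 20 might be meant as a whole-session rating.** The text does not say this, and HIIT has no matching end-of-session rating, so the arms would still differ.
- **Moving the rating does not make the arms fully comparable.** Exertion at the end of a 20-second bout and exertion in steady work differ in kind, and the HIIT walking recoveries are not rated at all. This stands and belongs with any comparison that is reported.

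**Conclusion.** The point holds as a timing fault in an ancillary measure. By the protocol's own figures, one of the two MCEET ratings at each rated session falls outside the work on either clock, and nothing elsewhere in the document repairs it. Any HIIT-versus-MCEET comparison of RPE that uses that rating would understate MCEET exertion. Confidence in the timing is high. The size is not derivable: 0.5 to 2.75 CR-10 points is an illustration that rests on the assumed ratings, on averaging the two, and on a constant rating through the work block.

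It goes no further than that. The adherence, fat-loss and mile-run comparisons are not directly affected. An effect on training is possible only if RPE is one of the measurements used to adjust intensity, and then only through sessions 6 and 9. It is worth correcting because the change is nearly free and the missing rating cannot be reconstructed.

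**What to change.** 1. Take the second MCEET rating at the end of the continuous block (session minute 17), before the cool-down begins. Keep the 10-minute rating and state that the clock starts with the warm-up.
2. Define interval for the HIIT ratings, as the 20-second bout if that is what is meant.
3. State that any between-arm comparison of RPE uses work-period ratings only, say how the ratings within a session are summarised, and note that bout-end and steady-state exertion are different quantities.
4. Reconcile the rating times with the session structure, and say which measurements the intensity-adjustment sentence refers to. That choice is the sponsor's.

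While the session structure is open, the HIIT total needs the same check: with five recoveries between six bouts it is 3 + 2 + 10 + 3 = 18 min, and it reaches 20 only if a sixth recovery follows the last bout.

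The cost is a few sentences in the protocol and one changed time on the participant's log. No visit, staff time or measurement is added.

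### Objective 2 compares the groups on fat loss and endurance, but the listed tests use no baseline covariate; ANCOVA on baselines already collected is a modest gain at no data cost, if assignment within pairs is random

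*Combined protocol and SAP*

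**What the plan says.** The analysis plan is one sentence in the last part of Methods. It opens "All the collected data will be statistically analyzed by Sigma Plot 12.0" and continues "using a two-way analysis of variance (ANOVA), Tukey's post hoc test, and a paired t-test". It does not name the two ANOVA factors, say whether either is a repeated measure, say what the t-test pairs, or assign a test to an outcome. The sample-size text adds only "Using ANOVA, match-paired study design, a minimum of 15 participants is required", again without factors.

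Research Objectives, item 2, asks for a between-group comparison of improvement in fat and endurance capacity. Methods provides the baselines for it: body composition by "air displacement plethysmography (Bod Pod) pre and post intervention (week 0 and 6", and a timed mile before and after the intervention.

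On assignment, Methods says "Participants will be match-paired based on their endurance capacity to either HIIT or MCEET group for five weeks" and, further on, "Each participant will be matched to either HIIT or MCEET group based on their timed one-mile run". It does not say how the two members of a pair are divided between the arms. The sample size allows for "34% of drop out rate" and ends at 20 per group.

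**The concern.** Objective 2 needs one estimate, the HIIT minus MCEET difference in fat and in mile time, and the plan does not say which listed test supplies it. Several analyses fit the wording:

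- **Group x time**, with time repeated. This fits best, because fat and mile time are measured twice.
- **Group x sex** on change. This is less likely: the sexes appear only as a recruitment count ("40 healthy adults aged 19 to 35 years (20 men, 20 women) will participate in the study") and no objective concerns sex.
- **A paired t-test across matched partners**, which the match-paired design suggests.
- **A pre-post paired t-test within each arm**, which does not compare the arms.

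The first three compare the groups and can be valid. None uses the measured baseline as efficiently as ANCOVA, and the partner test also discards every completer whose partner drops out. At stake is precision in a trial of 40 people, and a clear statement of which result answers Objective 2.

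**Working it through.** **Inputs from the documents (Methods).** 20 per group; alpha 0.05 (taken as two-sided); 34% dropout; primary-outcome difference 19.6 with SDs 9.4 and 19.1; stated minimum 15 at 95% power.

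**Assumed, because the documents give no figure.** Pre-post correlation rho of 0.5/0.7/0.9 (results are in that order throughout); equal SD before and after; a group difference of 0.5 SD; random assignment within pairs.

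**1. Does the plan's own figure reveal the intended test?** No sample size is given for Objective 2. The stated 15 for the primary outcome can be reached two ways:
- Unpaired: SD = sqrt((9.4² + 19.1²)/2) = 15.05. Then n = 2(1.960 + 1.645)² x (15.05/19.6)² = 15.3, so 16 per arm.
- Paired: taking 19.1 as the SD of pair differences, 19.6/19.1 = 1.026. A paired t-test then needs 14.4, so 15 pairs.

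The step to 20 is 15 x 1.34 = 20.1. Both routes land near 15, so the figure does not identify the analysis.

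**2. Group x time ANOVA against ANCOVA.** In a two-group pre-post design the interaction test is the comparison of change scores. In SD² units the residual variance is 2(1 - rho) for change and 1 - rho² for ANCOVA, a ratio of 2/(1 + rho). The SE of the group difference is sqrt(2 x variance/20), and power comes from the noncentral t with 38 df (change) or 37 df (ANCOVA).

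| rho | variance, change | variance, ANCOVA | ratio | power, change | power, ANCOVA |
|---|---|---|---|---|---|
| 0.5 | 1.00 | 0.75 | 1.33 | 34% | 43% |
| 0.7 | 0.60 | 0.51 | 1.18 | 51% | 58% |
| 0.9 | 0.20 | 0.19 | 1.05 | 93% | 94% |

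Simulation (12,000 runs) gave 34/51/93% against 42/56/94%. Equivalently, change scores with 20 per arm are about as precise as ANCOVA with 20(1 + rho)/2 = 15/17/19 per arm. Mean 95% CI half-widths are 0.64/0.49/0.285 SD against 0.56/0.46/0.281 SD. Group x sex on change behaves like the change score, at 35/51/93%.

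**3. Paired t-test across partners, mile time.** With no dropout, simulated power is 41/56/93% against 43/58/94% for ANCOVA, so pairing itself costs almost nothing. With 34% independent dropout, complete pairs number 20 x 0.66² = 8.7, while completers number 20 x 0.66 = 13.2 per arm. Power is then about 19/24/52% against 29/40/78% for ANCOVA on all completers; repeat runs agree within about two points. The loss comes mainly from dropout.

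**4. Why within-arm t-tests cannot answer Objective 2 (illustration only).** Suppose both arms truly gain the same amount g, in SD units. If p is the power of a paired t-test with 20 people and standardised effect g/sqrt(2(1 - rho)), exactly one arm is significant with probability 2p(1 - p).

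| common gain g | rho 0.5 | rho 0.7 | rho 0.9 |
|---|---|---|---|
| 0 | 9.5% | 9.5% | 9.5% |
| 0.1 | 13% | 16% | 27% |
| 0.2 | 23% | 31% | 50% |
| 0.3 | 37% | 47% | 31% |
| 0.5 | 49% | 34% | 0.6% |
| 0.8 | 14% | 2% | 0% |
| 1.0 | 2% | 0% | 0% |

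The range is about 0 to 50%, and the documents give no expected gain with which to place this trial in it.

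**5. If assignment is not random.** With no group effect and a baseline imbalance of 0.5 SD, the change-score and ANCOVA estimates differ by 0.5(1 - rho) = 0.25/0.15/0.05 SD. They then answer different questions.

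**The case against.** The strongest reply is that the plan names a two-way ANOVA, that repeated measurements make group x time its ordinary meaning, and that this test is valid. ANCOVA would then be a preference worth 7 to 9 points of power at rho 0.5 to 0.7, about one point at 0.9, and one or two points over partner pairing without dropout. It also depends on a randomisation that the documents do not state. All of this stands, and it limits the point to an efficiency gain plus a named test.

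Two stronger readings are tempting. A reader might infer that Objective 2 will be judged by significance in one arm and not the other. The documents do not support that: the ANOVA is listed beside the t-test, and the sample size is said to rest on an ANOVA. The table in step 4 shows only why the within-arm test must not carry that role. A reader might also infer that repeated scores will be entered as if independent. The text neither says nor suggests this, so no error rate is attached to it here.

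The objection does not remove the gap. Group x time does not explain the paired t-test, no contrast is named for Objective 2, and the baselines that ANCOVA needs are already collected.

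**Conclusion.** The point holds as a modest improvement that needs no new data; it does not show that the planned analysis is invalid. Against group x time, ANCOVA reduces variance by 25/15/5% (one minus (1 + rho)/2). Against a partner-paired t-test under independent 34% dropout the gain is larger, about 10 to 26 points of power. These sizes rest on the assumed correlations, the 0.5 SD difference, equal SDs and random assignment within pairs.

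Three limits apply. The gain over change scores is near zero when rho is high. ANCOVA does not apply to PACES or EARS, which have no pre-intervention score. Nor should a reader infer that it repairs dropout: in simulations with 24% dropout in HIIT and 44% in MCEET and no group effect, its type I error stayed near 5% when dropout depended on arm alone or on arm and baseline. It rose to 6.6-13.9% when dropout also depended on the change itself (change score 6.9-14.9%).

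**What to change.** In the statistical paragraph of Methods:

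- Make the Objective 2 test an ANCOVA of post-intervention body fat, and separately of mile time, on group and the participant's own baseline value of that outcome. Include everyone with a post value. Report the adjusted HIIT minus MCEET difference with its 95% CI.
- Name the factors of any ANOVA that is kept, and the unit of the paired t-test. Label within-arm pre-post t-tests as descriptive.
- State how the members of each pair are assigned to the arms. If this is not random, say in advance whether the difference in change or the baseline-adjusted difference is the target.

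The cost is a few sentences and a little analysis time. The ANCOVA is a linear regression on group and baseline, using measurements already scheduled.
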